2 ABBREVIATIONS

AASLD	- American Association for the Study of Liver Diseases
AE	- Adverse Event
ALF	- Acute Liver Failure
ALT	- Alanine aminotransferase
APAP	- n-acetyl-p-aminophenol (acetaminophen)
aPTT	- activated Partial Thromboplastin Time
AST	- Aspartate aminotransferase
AUC	- Area Under the Curve
BUN	- Blood Urea Nitrogen
CFR	- Code of Federal Regulation
CO ₂	- Carbon dioxide
CPDR	- Cumulative Percentage Dose Recovery (expressed as %)
CRA	- Clinical Research Associate
CRF	- Case Report Form
CRO	- Clinical Research Organization
CSPH	- Clinically Significant Portal Hypertension
CT	- Computed Tomography
CTCAE	- Common Terminology Criteria for Adverse Events
CVP	- Central Venous Pressure
DOB	- Delta over baseline
EASL	- European Association for the Study of the Liver
EC	- Ethics Committee
eCRF	- Electronic Case Report Form
EDC	- Electronic Data Capture
FDA	- Food and Drug Administration

Exalenz Bioscience Ltd.	Last update on: Nov 21, 2016
Study Title: Clinical Study of the BreathID[®] MCS System to train the algorithm for the ¹³C-Methacetin Breath Test (MBT) in assessment of Portal Hypertension in Patients with Compensated Liver Cirrhosis	Protocol No.: CSPH-EX-0414 Version: 1.5
Document N^o: CSD00076	Page 8 of 72

FHVP	- Free Hepatic Venous Pressure
GCP	- Good Clinical Practice
GI	- Gastrointestinal
GTTP	- Gamma-Glutamyl Transpeptidase
HCC	- Hepatocellular Carcinoma
HCO ₃	- Bicarbonate
HE	- Hepatic Encephalopathy
HVPG	- Hepatic Venous Pressure Gradient
ICH	- International Conference of Harmonization
IDE	- Investigational Device Exemption
INR	- International Normalized Ratio (for prothrombin time)
IRB	- Institutional Review Board
KOL	- Key Opinion Leaders
K+	- Potassium
LF	- Liver Function
MBT	- ¹³ C-Methacetin Breath Test
MCS	- Molecular Correlation Spectrometry
MELD	- Model for End-stage Liver Disease
Na+	- Sodium
NIH	- National Institute of Health
NPV	- Negative Predictive Value
NSBB	- Non-Selective Beta Blocker
OUS	- Out of the United States
O ₂	- Oxygen
PAP	- Pulmonary Artery Pressure
PEEP	- Positive End Expiratory Pressure
PHT	- Portal Hypertension

Exalenz Bioscience Ltd.	Last update on: Nov 21, 2016
Study Title: Clinical Study of the BreathID[®] MCS System to train the algorithm for the ¹³C-Methacetin Breath Test (MBT) in assessment of Portal Hypertension in Patients with Compensated Liver Cirrhosis	Protocol No.: CSPH-EX-0414 Version: 1.5
Document N°: CSD00076	Page 9 of 72

- PPV - Positive Predictive Value
- PDR - Percent Dose Recovered (expressed as % per hour)
- ROC - Receiver Operating Characteristic
- SAE - Serious Adverse Event
- SUSAR - Suspected Unexpected Serious Adverse Reactions
- TIPS - Transjugular Intrahepatic Portosystemic Shunt
- US - United States (of America)
- USA - United States of America
- WBC - White Blood Cells
- WHVP - Wedged Hepatic Venous Pressure

Exalenz Bioscience Ltd.	Last update on: Nov 21, 2016
Study Title: Clinical Study of the BreathID[®] MCS System to train the algorithm for the ¹³C-Methacetin Breath Test (MBT) in assessment of Portal Hypertension in Patients with Compensated Liver Cirrhosis	Protocol No.: CSPH-EX-0414 Version: 1.5
Document N^o: CSD00076	Page 10 of 72

3 PROTOCOL SYNOPSIS

Protocol Title: Clinical Study of the *BreathID[®] MCS* System to train the algorithm for the ¹³C-Methacetin Breath Test (MBT) in assessment of Portal Hypertension in Patients with Compensated Liver Cirrhosis

Protocol Reference Number: CSPH-EX-0414

Version and Date: v 1.5, 21 Nov, 2016

Phase of Development: Phase II (training)

Sponsor: **Exalenz Bioscience Ltd.**
[name]
[name]
[contact]
[contact]

Principle Investigators:

- a. [name] [name], Barcelona, Spain
- b. [name], Madrid, Spain
- c. [name], Toulouse, France
- d. [name], [name], Paris (Clichy), France
- e. [name], New Haven , CT , USA
- f. [name], Richmond, VA, USA
- g. [name], Bern, Switzerland
- h. [name], Durham, NC, USA

Institutions:

- a. Hospital Clinic, , Barcelona, Spain.
- b. Hospital Santiago Ramón y Cajal, Madrid, Spain
- c. Hopital Purpan, Toulouse, France
- d. Hopital Beaujon, Paris (Clichy), France
- e. Yale University School of Medicine, New Haven, CT / VA
Connecticut Health Care System, USA
- f. Virginia Commonwealth University Medical Hospital, VA, USA
- g. Inselspital University Hospital, Bern, Switzerland
- h. Duke University, Durham, NC, USA

Exalenz Bioscience Ltd.	Last update on: Nov 21, 2016
Study Title: Clinical Study of the BreathID[®] MCS System to train the algorithm for the ¹³C-Methacetin Breath Test (MBT) in assessment of Portal Hypertension in Patients with Compensated Liver Cirrhosis	Protocol No.: CSPH-EX-0414 Version: 1.5
Document N^o: CSD00076	Page 11 of 72

Investigated disease:	Clinically Significant Portal Hypertension (CSPH) in patients with compensated liver cirrhosis
Combination Product	BreathID [®] MCS system together with ¹³ C-labeled Methacetin
Comparator:	HVPG - Hepatic Vein Portal Pressure Gradient
Primary Objective:	The primary objective of the study is to develop an algorithm and its cut-off to detect CSPH, defined as HVPG ≥ 10 mmHg, based on the MBT.
Primary Efficacy	
Endpoint:	Binary diagnosis of CSPH, defined as HVPG ≥ 10 mmHg, correlated with an MBT result to be developed.
Secondary:	
 1. Binary diagnosis of portal hypertension with HVPG ≥ 12 mmHg 2. Binary diagnosis of portal hypertension with HVPG ≥ 20 mmHg 3. Correlation of MBT with HVPG readings 4. Assess the effect of beta blockers or other confounding factors on the Correlation of MBT with HVPG readings 5. Examine the effect of a single small (<3cm) HCC (hepatocellular carcinoma) on the correlation of MBT with HVPG tracings
Safety Endpoints:	Safety will be assessed by all adverse and serious adverse events occurring in all subjects enrolled throughout the duration of the study.
Study Design:	A multicenter, non-randomized, blinded, cross-sectional comparative exploratory study comparing various MBT measures to HVPG. This study will be used to train an algorithm using MBT measures and to select a cut-off to determine presence or absence of CSPH as defined by HVPG ≥ 10 mmHg.

Exalenz Bioscience Ltd.	Last update on: Nov 21, 2016
Study Title: Clinical Study of the BreathID[®] MCS System to train the algorithm for the ¹³C-Methacetin Breath Test (MBT) in assessment of Portal Hypertension in Patients with Compensated Liver Cirrhosis	Protocol No.: CSPH-EX-0414 Version: 1.5
Document N^o: CSD00076	Page 12 of 72

Study Population^a:

At least 200 consecutive compensated cirrhotic patients, defined as cirrhotic patients without complications^b and meeting all inclusion/exclusion criteria will be enrolled on a walk-in basis. If beta blockers or HCC or other confounding factors affect the correlation between MBT and HVPG the sample size may be enlarged following interim analysis.

Inclusion Criteria:

1. Adult men or women (≥ 18 years of age)
2. Patient (or legal guardian) can sign an Informed Consent Form
3. Known chronic liver disease with cirrhosis confirmed by either:
 - a. liver biopsy or
 - b. clinical (palpable left lobe, splenomegaly) and laboratory (platelets $< 150,000/\text{mm}^3$ or albumin $< 3.8\text{g/dL}$, or INR > 1.3) evidence of cirrhosis and/or
 - c. imaging studies by abdominal sonography, computer assisted axial tomography, or magnetic resonance imaging, showing a nodular liver and/or enlarged spleen and/or portosystemic collaterals with portal vein patency and/or minimal ascites, and/or colloid shift on a colloid-isotope liver-spleen scan or measurements of liver stiffness suggestive of cirrhosis
4. Europe: Indicated to undergo HVPG testing
US: Consented for HVPG
5. Can tolerate an overnight (8-hour) fast
6. For patients treated with statins: They have to be on a stable dose for at least 4 weeks prior to any study related tasks (MBT or HVPG measurement)
7. For patients treated with beta blockers: They have to be on a stable dose for at least 6 weeks prior to any study related tasks (MBT or HVPG measurement)

^a Most patients to be enrolled in the proposed study will be from centers in Europe. Based on expert opinion in the field of hepatology, the population to be enrolled from Spain and France is representative of patients with chronic liver disease in the United States. The management of patients in the United States is based upon and derived from the experience and guidelines developed in Barcelona (Spain). Patients in these countries have similar etiologies and prognosis and are being used interchangeably in multicenter clinical trials using HVPG testing

^b See eligibility criteria.

Exalenz Bioscience Ltd.	Last update on: Nov 21, 2016
Study Title: Clinical Study of the BreathID[®] MCS System to train the algorithm for the ¹³C-Methacetin Breath Test (MBT) in assessment of Portal Hypertension in Patients with Compensated Liver Cirrhosis	Protocol No.: CSPH-EX-0414 Version: 1.5
Document N^o: CSD00076	Page 13 of 72

8. For patients who stopped their treatment with beta blockers: Their last dose should be at least 6 weeks prior to any study related tasks (MBT or HVPG measurement)

Note: In case patient has HCC, breath test has to be performed on the day of HVPG measurement.

Exclusion Criteria:

1. Decompensated cirrhosis as clinically defined by the occurrence of any of the following: ascites, hepatic encephalopathy, variceal bleeding (active upper GI bleeding) or hepatorenal syndrome
2. Renal failure (creatinine > 2.5 mg/dl)
3. Known acute renal tubular disease
4. Known hypotension (Systolic Pressure <100mmHg)
5. Hypocoagulability defined as PT >6 and INR >2.3.
6. Congestive heart failure (assessed clinically as NIHA >2)
7. Known pulmonary hypertension (right ventricular systolic pressure > 45 mm Hg)
8. Uncontrolled diabetes mellitus (HBA1C >9.5gr%)
9. Concurrent prednisone or immunosuppressive treatment, if therapy and/or response to treatment are not stable for at least 3 months.
10. Documented hepatocellular carcinoma lesion larger than 3cm and/or multifocal lesions and/or evidence of vascular invasions
11. Gastric bypass surgery or extensive small bowel resection
12. Total parenteral nutrition
13. Any organ transplant recipient
14. Pregnant or breast feeding
15. Allergy to acetaminophen and/or other related medications.
16. Documented drug-related concurrent hepatotoxicity or drug-related silent steatosis or drug-related fibrosis (e.g. amiodarone, methotrexate and tamoxifen)
17. Uncontrolled malabsorption or diarrhea
18. Documented non-cirrhotic PHT, partial/complete portal venous occlusion, hepatic venous occlusion, previous PHT surgery, or placement of a transjugular intrahepatic portosystemic shunt (TIPS)
19. Primary or secondary biliary cirrhosis, primary or secondary sclerosing cholangitis, hepatic sarcoidosis, or other cholestatic disorders
20. Subjects unable to perform the MBT within 7 days of HVPG procedure.

Exalenz Bioscience Ltd.	Last update on: Nov 21, 2016
Study Title: Clinical Study of the BreathID[®] MCS System to train the algorithm for the ¹³C-Methacetin Breath Test (MBT) in assessment of Portal Hypertension in Patients with Compensated Liver Cirrhosis	Protocol No.: CSPH-EX-0414 Version: 1.5
Document N^o: CSD00076	Page 14 of 72

21. Subject should not have taken any of the following for at least 48 hours prior to the breath test: Acyclovir , allopurinol, carbamazepine, cimetidine, ciprofloxacin, daidzein, (herbal) disulfiram, echinacea, enoxacin, famotidine, fluvoxamine, methoxsalen, mexiletine, montelukast, norfloxacin, phenylpropanolamine, phenytoin, propafenone, rifampin, terbinafine, ticlopidine, thiabendazole, verapamil, zileuton or any medication that might interfere with Methacetin metabolism or might affect CYP 1A2
22. Subject should not have taken amiodarone within the last 30 days prior to the breath test or HVPG procedure. Splenomegaly secondary to inflammation/infection or hematologic malignancy.
23. Last dose of HCV treatment received within the past 3 years

On the day of the MBT:

1. 8 hours fasting prior to MBT including all PO morning medications
2. No Smoking on the day of the MBT
3. No caffeine within 24 hours prior to MBT
4. No paracetamol (acetaminophen) based medications within 24 hours prior to MBT
5. No general anesthesia or sedation within 24 hours prior to MBT
6. No alcohol within 24 hours prior to MBT
7. Patient should be symptom free of any prior intervention (e.g. biopsy)

Listing of Study Procedures:

1. IC and eligibility
2. Baseline and Physical Examination
3. HVPG procedure^c
4. MBT - ¹³C-Methacetin Breath Test (within 7 days of HVPG)

Note1: The MBT may be performed prior to HVPG as long as it is done within 7 days.

Note2: If patient is using a stable dose of beta blockers both the MBT and the HVPG procedures should be performed while continuing the stable dose even on the morning of each test.

Note3: If patient has HCC, breath test has to be performed on the day of HVPG measurement.

^c The measurement will be performed in a uniform way including following a standardized procedure to measure HVPG pressures (see Appendix II), either before or after the MBT, with certain limitations detailed in the protocol.

Exalenz Bioscience Ltd.	Last update on: Nov 21, 2016
Study Title: Clinical Study of the BreathID[®] MCS System to train the algorithm for the ¹³C-Methacetin Breath Test (MBT) in assessment of Portal Hypertension in Patients with Compensated Liver Cirrhosis	Protocol No.: CSPH-EX-0414 Version: 1.5
Document N^o: CSD00076	Page 15 of 72

Rules of discontinuations (Subject and/or Study):

1. Withdrawal of patients from the study if they have a CTCAE (Common Terminology Criteria for Adverse Events) Grade 3 or higher regardless of whether the event is attributed to the drug unless it is caused by an accident that could not reasonably be attributable to the drug (CTCAE: Common Terminology Criteria for Adverse Events Version 4.0).
2. Discontinuance of study, if ≥ 2 patients on Methacetin develop the same CTCAE Grade 3 event or 1 patient develops a CTCAE Grade 4 or higher event due to the breath test.

Data Analysis / Statistics:

A ROC analysis will be used to determine the optimal parameter and cut-offs for required performance measures sensitivity and specificity.

All efficacy analysis will include the point estimates of sensitivity, specificity, PPV and NPV with respective exact 95% confidence intervals. The respective Positive and Negative Predictive Values (PPV and NPV) will be presented as a function of possible CSPH prevalence and will include the prevalence of the enrolled population.

Exalenz Bioscience Ltd.	Last update on: Nov 21, 2016
Study Title: Clinical Study of the BreathID[®] MCS System to train the algorithm for the ¹³C-Methacetin Breath Test (MBT) in assessment of Portal Hypertension in Patients with Compensated Liver Cirrhosis	Protocol No.: CSPH-EX-0414 Version: 1.5
Document N^o: CSD00076	Page 16 of 72

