12.7.5 Performance Analysis

A model/algorithm will be developed for the differentiation between subjects with and without CSPH, defined as HVPG ≥ 10 mmHg. It will be developed using either logistic regression or neural network or any other known methodology. Using a cut-point on the score a binary diagnosis of CSPH (Y/N) will be obtained. The minimal criterion for sufficient efficacy is an Area under the Receiver Operating Curve (AUC) ≥ 0.85 in this patient population. A potential clinical utility was designated for the algorithm/model output; where this algorithm could aid the clinician in ruling-out CSPH. This will be translated into finding a model prediction cut-point that provides a high sensitivity (true positive rate) and at least moderate specificity (true negative rate), which in turn achieves a high negative predictive value (NPV). High NPV is considered to be near 90% (i.e. 88%) thus sensitivity should be at least 90% and specificity should be at least 50%. Cross validation methods will be used to test algorithm stability.

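### The exact 95% interval for specificity is too narrow as a statement of the specificity available at 90% sensitivity, because the cut-off is placed on the same patients

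*Combined protocol and SAP*

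**What the plan says.** Protocol synopsis, Data Analysis / Statistics: "A ROC analysis will be used to determine the optimal parameter and cut-offs for required performance measures sensitivity and specificity". The next paragraph says that the efficacy analysis will give "point estimates of sensitivity, specificity, PPV and NPV with respective exact 95% confidence intervals". It adds that PPV and NPV "will be presented as a function of possible CSPH prevalence and will include the prevalence of the enrolled population"; no interval method is named for that display. The synopsis says only exact. The term exact binomial appears in section 12.7.4, for adverse events, but Clopper-Pearson is the natural reading here too.

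Section 12.7.5 sets the rule-out goal, with NPV near 90% (88% is named): "sensitivity should be at least 90% and specificity should be at least 50" per cent. On the algorithm: "It will be developed using either logistic regression or neural network or any other known methodology". Cross-validation is to test stability and is not tied to any reported estimate or interval.

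Section 12.5 plans 200 subjects with at least 50 CSPH-positive and at least 50 CSPH-negative. Section 12.7.1 makes the performance analyses descriptive. Sections 12.1 and 12.2 send the algorithm and its cut-off to a separate validation study.

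**The concern.** Two questions can be asked of a specificity reported from this study:

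- (a) What is the true specificity at the cut-off that was actually picked?
- (b) What specificity does the test offer at 90% sensitivity?

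Section 12.7.5 sets its requirement in the terms of (b). An exact binomial interval counts only the sampling error among the CSPH-negatives. For (b) there is a second error: the positives determine the cut-off, and in a sample of 50 to 150 positives the observed 90% point can lie well away from the true one. Nothing in the plan says that the intervals allow for this.

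At stake is the reading of the 50% floor. A narrow interval lying above 50% would suggest that the requirement is securely met when the data do not show it.

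**Working it through.** **The plan's own precision figure.** Section 12.5 gives a half-width of 0.1 for AUC 0.85 at N = 200. Using the Hanley-McNeil variance with A = 0.85, Q1 = A/(2−A) = 0.739, Q2 = 2A²/(1+A) = 0.781:

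- 150 positives, 50 negatives: half-width 0.053.
- 25 and 175 (1:7): 0.097.
- 22 and 178 (1:8): 0.103.

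So 0.1 reproduces as roughly the worst case. It concerns the AUC; the plan states no precision for specificity.

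**Assumptions.** Equal-variance binormal score, AUC 0.85, one score chosen in advance. Separation d = √2·Φ⁻¹(0.85) = 1.466. The true 90%-sensitivity cut-off is c = 1.466 − 1.282 = 0.184, so true specificity there is Φ(0.184) = 57.3%. The three mixes below all meet the minimum of 50 per group.

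**Hand approximation for question (b).** The variance of observed specificity at observed 90% sensitivity is about

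Sp(1−Sp)/n + [φ(c)/φ(c−d)]² · Se(1−Se)/m,

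with m positives and n negatives. Here φ(c)/φ(c−d) = 0.392/0.1755 = 2.235, squared 4.995. The exact interval reflects only the first term. Approximate coverage is 2Φ(1.96·√first/√total) − 1.

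| m / n | first term | second term | share from cut-off | approx. coverage |
|---|---|---|---|---|
| 50/150 | 0.00163 | 0.00899 | 85% | 56% |
| 100/100 | 0.00245 | 0.00450 | 65% | 76% |
| 150/50 | 0.00489 | 0.00300 | 38% | 88% |

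**Simulation (20,000 trials per mix).** The cut-off is the highest with observed sensitivity of at least 90%, with Clopper-Pearson intervals at that cut-off.

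| m / n | mean exact width, Sp | 3.92 × SD of observed Sp | coverage (b), Sp | coverage (a), Sp |
|---|---|---|---|---|
| 50/150 | 0.159 | 0.378 | 58% | 96% |
| 100/100 | 0.198 | 0.317 | 77% | 96% |
| 150/50 | 0.282 | 0.341 | 89% | 97% |

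At 50/150 the printed half-width is about 8 points, while observed specificity has a 95% range of 39% to 77%.

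**Effect on the 50% floor.** If true specificity at 90% sensitivity is exactly 50%, the lower exact limit should exceed 50% in about 2.5% of trials. It does so in about 28% (50/150), 13% (100/100) and 5 to 6% (150/50).

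**Other measures, one score, question (a).** Coverage is 96.4–97.0% for sensitivity, 98.2–98.9% for NPV and 99.7–99.9% for PPV. None is too narrow. Against question (b), NPV coverage is about 100%, and PPV 89.3%, 95.2% and 98.2% across the three mixes.

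**Selection and fitting, question (a), apparent results.**

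- Best of 5 to 10 correlated parameters: specificity coverage 89.7–94.9%.
- Linear discriminant, one informative predictor and the rest noise (assumption). With 5 predictors, specificity covers 94.1–96.0%. With 10, specificity covers 90.8–92.8%, sensitivity 88.7–90.0% and NPV 92.5–93.6%. With 20, specificity covers 74–81%, sensitivity 66–70%, NPV 69–72% and PPV 87–89%.
- Much of the 20-predictor loss is optimism in the estimate. At 100/100, apparent against true specificity is 0.659 v 0.602, and NPV 0.867 v 0.796.

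**Testing the remedy.** A percentile bootstrap that re-places the cut-off in each resample covers specificity for (b) in about 92% to 96% of trials. For NPV at the chosen cut-off the same bootstrap covers only about 63% to 78%. Each resample resets apparent sensitivity to about 90%, so the sensitivity error disappears; at 100/100 the mean NPV width falls from 0.18 to 0.08.

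**NPV by prevalence.** With prevalence p, logit(NPV) = ln[Sp/(1−Se)] + ln[(1−p)/p], with variance Se/[(1−Se)m] + (1−Sp)/(Sp·n). At Se 90%, Sp 50% and 100/100, the variance is 0.09 + 0.01 = 0.10 (SE 0.316). At p = 40%, NPV is 0.882 (0.801–0.933); at 60%, 0.769 (0.642–0.861). With one score this interval covers 95.4–96.4% at the chosen cut-off.

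**The case against.** The strongest reply is that the plan picks a cut-off, reports performance at it, and validates it elsewhere. The matching quantity is then (a), and for one pre-chosen score the exact intervals are sound. That stands, and it limits the point. But section 12.7.5 also uses the results to judge whether the required specificity is available at the required sensitivity. An unlabelled interval will be read as answering that.

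A reader might infer that all four promised intervals are too narrow. The calculations do not support this: with one score, NPV and PPV over-cover at the chosen cut-off. The broader failure needs parameter selection or a heavily fitted model. Section 12.7.5 permits either, but the plan gives no number of predictors.

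A reader might also infer that the enrolled-prevalence interval will be carried over to other prevalences, or that no interval exists there. The synopsis says neither. The prevalence display is a separate sentence that promises no interval, and usable methods exist. The gap is an unspecified method.

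Nor do the documents say that the decision to lock the cut-off or fund validation rests on these intervals; the stated criteria are an AUC of at least 0.85 and point floors. Finally, 50/150 is the most adverse mix shown. The sponsor's earlier data (section 5.6) had 51 CSPH-positives among 58, nearest to 150/50, where coverage is 89%.

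**Conclusion.** The point holds for specificity at 90% sensitivity. Under a binormal score with AUC 0.85 and one pre-chosen parameter, the nominal 95% interval covers about 58%, 77% and 89% at the three mixes. The shortfall is greatest when positives are few. It does not extend to NPV or PPV at the chosen cut-off with a single score. If a parameter is selected or many predictors are fitted and apparent results are reported, estimates and intervals can be wrong for all four measures. The size of that error depends on modelling choices the plan leaves open.

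The separate validation study and the descriptive status lower the severity. The change is still worth making, because a descriptive interval should reflect the uncertainty it appears to describe.

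**What to change.** 1. Report specificity at 90% sensitivity with a percentile bootstrap interval that repeats cut-off placement, and any parameter or model selection, in every resample.
2. Keep exact intervals for performance at the locked cut-off, labelled *cut-off treated as fixed*. Where a parameter or model was selected, base the estimates on nested cross-validation or optimism-corrected bootstrap predictions; widening an interval around an optimistic estimate does not cure it.
3. Do not use the cut-off-re-placing bootstrap for NPV or PPV. For PPV and NPV by prevalence, name an interval that combines the errors in sensitivity and specificity at the locked cut-off, for example the logit delta method, and list the prevalences to be shown.

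The cost is SAP wording and programming, and a wider interval for specificity. No patients or procedures are added.
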